6.4. Data Presentation Conventions

A table of contents, at the end of this SAP, provides the expected titles and numbers of the tables, listings, and figures of the final report. Changes to titles or numbering in the final report will not necessitate a revision to the SAP, nor will it be considered a deviation from planned analyses. Additional data listings supporting the tables will not be considered a deviation from the planned analyses.

6.5. Analysis Populations

The populations used for data analysis of this study are defined below.

6.5.1. Screened Subjects

Screened subjects are those subjects who are screened for this study and are either screen failures or treated.

6.5.2. Screen Failures

Subjects who provide informed written consent but do not receive study treatment are considered screen failures.

6.5.3. Safety Population

The Safety population is defined as all subjects who receive at least one dose of study medication. This population will be used in the assessment and reporting of safety data. In addition, efficacy summaries will be based on this population.

6.6. Baseline Definition

For a given subject and assessment, baseline will generally be defined as the latest non missing result prior to administration of the first dose of study drug. If a subject is enrolled, but fails to receive study drug, baseline will be the last non-missing result.

The baseline ECG values will be the average of the triplicate ECG readings obtained on Day 1 (or screening if the Day 1 average is missing).

6.7. Derived and Transformed Data

6.7.1. Baseline Age

The subject's baseline age in years will be the age provided in the eCRF as collected at the time of informed consent.

6.7.2. Study Day

If the date of interest occurs on or after the date of the first dose, then study day will be calculated as (date of interest – date of first dose) + 1. If the date of interest occurs prior to the

first dose date, then study day will be calculated as (date of interest – date of first dose). There is no study day 0.

6.7.3. Change from Baseline, Percent Change from Baseline and Ratio to Baseline

The following changes from baseline will be derived:

- Change from baseline will be calculated as (post-baseline result baseline result)
- Percent change from baseline will be calculated as (change from baseline/baseline result * 100)
- Ratio to baseline will be calculated as post-baseline result divided by baseline result

If either the baseline or the post-baseline result is missing, then the changes from baseline described above will be missing. If the baseline value is 0, the percent change from baseline or ratio to baseline will be missing.

Note: The CKD-EPI formula will use the serum creatinine in the computation of eGFR included in the efficacy summary table.

6.7.4. Fold Change

Fold change from the ULN will be calculated as (result/ULN), and fold change from the LLN will be defined similarly as (result/LLN).

6.7.5. Questionnaire Assessments

Scale scores and total scores resulting from questionnaire assessments will be calculated per the official assessment guidelines. Details are provided in Section 14.3.

6.7.6. Visit Windows

Visit windows will not be applied.

6.7.7. Multiple Assessments in a Visit Window

Visit windows will not be applied.

For lab parameters where a central lab and local lab were collected at the same scheduled visit, the central lab value will be used. Local lab will be used if central lab data are not available.

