12.11.5. Clinical Chemistry, Hematology, Urinalysis, and Other Laboratory Assessments

[figure not shown]
Blood and urine samples will be obtained per the schedule of assessments as specified in Table 2 and Table 3. Individual laboratory tests are provided in Table 5.

In general, laboratory samples collected at visits to the investigative site should be collected using kit supplies provided by the central laboratory. However, at the investigator's discretion, local laboratories may be used in place of the central laboratory (eg, for logistical reasons such as delays in transport due to COVID-19) or for analysis of samples collected for assessment of possible AEs (eg, when emergent safety concerns require expedited turnaround times for safety laboratory assessments). The additional renal and hepatic safety assessments may be performed at the investigative site or at a local laboratory more convenient for the subject or via a home health service. The results from laboratory testing performed at a local laboratory must be provided to the investigational site. The use of a local or remote laboratory in this manner, and any differences in analyte panels with the central laboratory, based on the availability of testing at the local or remote laboratory, will not be considered protocol deviations for the purposes of this protocol. Reference ranges for each local or remote laboratory used will be provided to the sponsor and included in data listings.

Results from laboratories should be reviewed as received by the investigator. Evidence of this review should be provided in the source records and may include printing of the laboratory reports with a signature attesting to a review. For out-of-range findings, the interpretation of clinically significant or not clinically significant should be denoted in the source records. Clinically significant laboratory findings in the opinion of the investigator should be recorded as AEs and handled as described in the protocol (Section 13).

Table 6: Clinical Laboratory Evaluations

| Table 6. Chinear Laboratory Evaluations | | |
|---|---|--|
| Chemistry | Coagulation | |

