10.4. Routine Laboratory Data

An assessment of drug induced liver injury (DILI) for elevations in liver function tests will be performed. For ALT, AST, total bilirubin and international normalized ratio (INR) within a dosing group, the maximum post-baseline value across a subject's visits (scheduled and unscheduled, out to 30 days post dose) will be determined for each test. The maximum value for each parameter will then be summarized per the categories given below:

ALT/ AST/ ALT and AST/ ALT or AST	Total Bilirubin	INR	ALT or AST and Total Bilirubin
> 1.5X ULN > 3X ULN > 5X ULN > 10X ULN > 20X ULN	> ULN > 1.5X ULN > 2X ULN	> 1.5	ALT > 3X ULN and Total Bilirubin > 1.5X ULN ALT > 3X ULN and Total Bilirubin > 2X ULN AST > 3X ULN and Total Bilirubin > 1.5X ULN AST > 3X ULN and Total Bilirubin > 2X ULN (ALT > 3X ULN or AST > 3X ULN) and Total Bilirubin > 1.5X ULN (ALT > 3X ULN or AST > 3X ULN) and Total Bilirubin > 2X ULN (ALT > 3X ULN or AST > 3X ULN) and Total Bilirubin > 2X ULN)

Within a specific outcome (eg, ALT, AST, etc.), the categories are descending cumulative and not mutually exclusive.

In addition, for serum creatinine, within a dosing group, the maximum post-baseline value across a subject's visits (scheduled and unscheduled, out to 30 days post dose) will be determined. The maximum value will then be summarized by dosing group for the categories given below:

- > ULN but $\leq 1.5 \times$ ULN
- $> 1.5 \times ULN \text{ but } < 3 \times ULN$
- $\geq 3 \times ULN$
- ≥ 0.3 mg/dL increase from baseline.

Laboratory abnormalities will be graded according to CTCAE (Version 5.0, 27 November 2017). Any graded abnormality that occurs following the initiation of study drug (within 30 days post last dose) and represents at least 1-grade increase from the baseline assessment is defined as treatment emergent. A listing of all liver function test results for subjects experiencing a treatment-emergent Grade 3 or 4 liver function test will be provided.

All laboratory data will be listed.

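### The SAP's central-over-local laboratory rule has no exception for worst-value summaries, so the liver and creatinine maximum tables can leave out a higher local result paired with a central one

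*SAP*

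**What the plan says.** SAP 6.7.7 sets the rule for a parameter that has results from both laboratories at one scheduled visit, and for the reverse case: "the central lab value will be used. Local lab will be used if central lab data are not available". The rule covers laboratory parameters in general and names no output to which it does or does not apply.

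SAP 10.4 defines the laboratory safety tables. For ALT, AST, total bilirubin and INR, "the maximum post-baseline value across a subject's visits (scheduled and unscheduled, out to 30 days post dose) will be determined for each test". Creatinine is handled the same way: "In addition, for serum creatinine, within a dosing group, the maximum post-baseline value across a subject's visits", again over scheduled and unscheduled visits. The section settles which visits count but is silent on which laboratory counts. It also defines treatment-emergent CTCAE grades and ends: "All laboratory data will be listed".

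Protocol 12.11.5 lets the investigator use a local laboratory for logistical reasons, or for possible adverse events, for example "when emergent safety concerns require expedited turnaround times". Protocol 13.5.1 allows repeat testing after an ALT above 3 x ULN to be done locally.

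**The concern.** A rule preferring one laboratory suits a by-visit mean, where each subject should contribute one comparable value. A worst-value table asks a different question: how high did the subject's result go? Removing one of two valid readings before taking the maximum changes the answer in one direction only, downward.

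SAP 5.2 says the abbreviated report will focus on safety. Tables 14.3.2.1 and 14.3.2.2 are the only laboratory safety tables in the SAP's display list. The top creatinine category, at or above 3 x ULN, is the same level that Protocol 7.4.1 and 7.4.3 use, so a subject's place relative to it will be read closely. With 2 treated subjects, moving one across a category changes the all-doses proportion by 1/2, or 50 percentage points. If grading also follows 6.7.7, Listing 16.2.8.6, which is restricted to subjects with a treatment-emergent Grade 3 or 4 liver test, could omit a subject.

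**Working it through.** The plan gives no figure on this point, so there is nothing to reproduce. The check sets the two sections side by side and then illustrates the consequence.

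**1. Which results reach the maximum if both sections are followed literally**

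| Result | Treatment under 6.7.7 and 10.4 |
|---|---|
| Central only, scheduled visit | Counts |
| Local only, scheduled visit (for example Weeks 3, 5, 6, 7, 10) | Counts |
| Unscheduled visit, either laboratory | Counts; 6.7.7 covers scheduled visits only |
| Central and local, same scheduled visit | Central counts, local does not |

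Only the last row is affected. The maximum of a subset cannot exceed the maximum of the full set, so the tabulated value is the same or lower.

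**2. Invented example (not trial data), creatinine as a multiple of ULN**

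- Week 2: central 1.2.
- Week 4: central 2.8, local 3.1.
- Week 5: local only 1.6.
- Week 8: central 1.4.

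Under 6.7.7 the maximum is max(1.2, 2.8, 1.6, 1.4) = 2.8, in the category above 1.5 and below 3 x ULN. With all results it is 3.1, in the category at or above 3 x ULN.

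**3. A pair near a category boundary**

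Let t be the true value divided by the cut-off, and assume that both laboratories have independent normal errors with the same CV (the documents give none). The chance that one reading reaches the cut-off is p = Φ((t − 1)/(CV × t)). The chance that the local reading reaches it and the central one does not is p(1 − p).

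- t = 1.00, any CV: p = 0.50, so 0.50 × 0.50 = 25%.
- t = 1.05, CV 5%: 0.05/0.0525 = 0.95, p = 0.83, so 0.83 × 0.17 = 14%.
- t = 0.98, CV 5%: −0.02/0.049 = −0.41, p = 0.34, so 0.34 × 0.66 = 22%.
- t = 1.10, CV 5%: 0.10/0.055 = 1.82, p = 0.965, so about 3%.
- t = 0.90, CV 5%: −0.10/0.045 = −2.22, p = 0.013, so about 1%.

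These figures are conditional on a pair existing, and on no other visit having already put the subject in the category.

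**4. Chance that the overall maximum is a dropped value**

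If all of a subject's values were exchangeable (an assumption), with n values kept and m local duplicates dropped, the chance is m/(n + m). The protocol schedules chemistry at 13 post-baseline visits to Week 24 plus follow-up (n = 14), or 20 visits to Week 52 plus follow-up (n = 21).

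| n | m = 1 | m = 2 | m = 4 |
|---|---|---|---|
| 14 | 1/15 = 6.7% | 2/16 = 12.5% | 4/18 = 22.2% |
| 21 | 1/22 = 4.5% | 2/23 = 8.7% | 4/25 = 16.0% |

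The actual m is unknown and may be zero.

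**The case against.** The strongest reply is that 10.4 is the specific provision and already means every value, while the scheduled-visit wording of 6.7.7 fits the by-visit efficacy table, which includes creatinine-based eGFR. That reading is possible, but neither section states it. Two programmers could produce different tables from the same SAP, which is itself a reason to add a sentence.

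Preferring the central laboratory also has merit: Protocol 5.4.1 uses one to standardise safety data, and a maximum over duplicate readings is biased slightly upward. This stands as a cost of the fix, and it bears most on the absolute criteria. A local creatinine set against a central baseline could produce a false rise of 0.3 mg/dL or more.

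Practical impact is limited too. Two subjects' listings can be read by hand, so a local value is left out of a summary and not lost from the report. This lowers the importance of the point without removing it.

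A reader might infer that a peak measured only at a local laboratory would vanish. The documents say the opposite: 6.7.7 uses the local value when there is no central one. A reader might also infer that local samples are taken chiefly at safety peaks, so that the dropped value is usually the highest. Protocol 12.11.5 does not support this. It also cites logistics, and much of what it describes is substitution, which yields a local-only value that is kept. With equal errors, the central reading of a pair is the higher one as often as the local one.

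**Conclusion.** The point holds as a gap between two SAP sections. As written, a higher local result paired with a central result at the same scheduled visit does not enter Tables 14.3.2.1 and 14.3.2.2, and possibly not the treatment-emergent grading behind Listing 16.2.8.6. The tables can understate the maximum; the documents do not show that they do, because they do not show that any such pair exists.

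The direction is certain and the size is not known. The 25% figure is for a pair exactly at a boundary with independent, equal and symmetric errors. It is not an estimate of how often subjects would be misclassified. Nor do the documents support inferring that the protocol's discontinuation or study-stopping criteria are weakened: 6.7.7 governs analysis outputs, and those criteria are applied by the investigator and the renal working group during the study.

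Given a safety-focused report and a nearly free correction, the change is worth making.

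**What to change.** 1. In SAP 6.7.7, limit the central-over-local preference to by-visit summaries.
2. In SAP 10.4, state that all central and local results count towards the maximum and towards treatment-emergent grading. Where a category is a multiple of ULN, use the ULN of the laboratory that produced the result. Protocol 12.11.5 already has local reference ranges sent to the sponsor.
3. Scaling by ULN does not help with the two absolute criteria, INR above 1.5 and a creatinine rise of at least 0.3 mg/dL. For these, footnote any value that comes from a local laboratory or that compares a local result with a central baseline.

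The cost is a short SAP edit, two footnotes and minor programming for 2 subjects. The downside is a slight upward bias from taking the maximum of duplicate readings, and the chance that a spurious local value enters a table. The listings would show such a value.

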6.8. Handling of Missing Data

6.8.1. Missing Efficacy Endpoints

Not applicable.

6.8.2. Missing Start and Stop Dates for Prior and Concomitant Medication

An incomplete time has either the hours or minutes missing, but not both; or a time may have hours and minutes but be recorded on a 12-hour clock and AM/PM cannot be determined from other information. For calculation purposes, incomplete times will be treated as completely missing.

If the medication start date is completely missing and the medication stop date is after the start date of the first dose of study drug (or the medication is ongoing) then the medication will be considered concomitant. If both dates being compared are present and either or both times are missing, then dates alone will be compared.

An incomplete date has at least one of the day, month, or year unknown, but at least one is present. For analysis of medications, a complete date should be established to identify medication as occurring during treatment or not. For the purposes of handling partially reported start and stop dates for medication, the following algorithm will be applied:

• Missing start day, but month and year present:

If study medication had been taken in the same month and year as the occurrence of the medication, then the start day of the medication will be assigned to the day of first dose of study medication.

Otherwise, the start day will be set to the first day of the month.

• Missing start day and month, but year present:

If study medication had been taken in the same year as the occurrence of the medication, then the start date of the medication will be assigned to the date of first application of study medication.

Otherwise, the start day and month will be set to 01 January.

- Missing end day, but month and year present:
 - The day will be set to the last day of the month.

• Missing end day and month, but year present:

The end day and month will be set to the date of trial termination for the subject.

If after following the steps above, an imputed start date comes after an end date (either actual or imputed), the start date will be imputed to be equal to the end date.

In subject data listings, start and stop date of medication will be displayed as reported on the eCRF.

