6.8.3. Missing Start and Stop Dates for Adverse Events

The same conventions to address incomplete dates for prior and concomitant medications (see Section 6.8.2 above) will also be used for AEs.

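### SAP 6.8.2 does not keep imputed dates inside the recorded year or month: wrong as written, but with little expected effect in this study

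*SAP*

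**What the plan says.** SAP 6.8.2 sets out the partial-date algorithm for medications. SAP 6.8.3 states that the same conventions "will also be used for AEs". Four rules matter here.

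- **Year-only start.** The trigger is "If study medication had been taken in the same year as the occurrence of the medication", and "then the start date of the medication will be assigned to the date of first application of study medication". If there was no dosing in that year, the start becomes 1 January.
- **Year-only stop.** "The end day and month will be set to the date of trial termination for the subject".
- **Start with the day missing.** The trigger is "If study medication had been taken in the same month and year as the occurrence of the medication", and "then the start day of the medication will be assigned to the day of first dose of study medication". Otherwise the first of the month is used.
- **Consistency check.** If an imputed start falls after the end date, "the start date will be imputed to be equal to the end date".

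The dates then decide whether a medication is prior (SAP 8.7) or concomitant (10.3), whether an adverse event is treatment-emergent (10), and which dosing group a record belongs to (10, 10.3). Listings show dates as entered (6.2, 6.8.2).

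**The concern.** Both start rules are triggered by any dosing in the recorded period, but the value they assign comes from the first dose. The two agree only when the first dose itself falls in that period. The stop rule does not say whether the recorded year survives. The single consistency check compares start with end and never with the recorded year or month. A programmer who follows the text can therefore produce a date that the case report form rules out.

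At stake is the placement of records in the concomitant-medication and adverse-event tables, in a report that SAP 5.2 says will focus on safety. SAP 7.1 states that both treated subjects started on 500 mg BID, and 10.3 speaks of a single subject with two dosing groups. The 500 mg Total Daily Dose column thus appears to hold one subject. Moving that subject's only record of an event changes the cell from 1/1 to 0/1.

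**Working it through.** The SAP gives no figure to reproduce, so the check applies its rules to illustrative dates.

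**Assumptions (the documents give no subject dates).** Dosing lasts 150 days, the second dosing group starts on day 61, and termination is 28 days after last dose. First dose is 20 Feb 2022, 20 Sep 2021 or 31 Mar 2022. The last doses are then 19 Jul 2022, 16 Feb 2022 and 27 Aug 2022, and the terminations 16 Aug, 16 Mar and 24 Sep 2022.

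**1. Year-only start.** Take first dose 20 Sep 2021.
- On-treatment days in 2022: 31 in January + 16 in February = 47. Each onset recorded as 2022 is imputed to 20 Sep 2021. That contradicts the record on 47/150 = 31.3% of on-treatment days.
- The second dosing group starts on 19 Nov 2021, so all 47 move from the second group to the first.
- These onsets were already after first dose, so they normally stay treatment-emergent and the Total All Doses column does not change.
- Medications likewise stay concomitant. SAP 10.3 allocates them by when they were taken, so one that runs on gains an extra entry in the first group's column.
- How often the condition arises: with first doses spread evenly over the year, an n-day course crosses 31 December for n − 1 of 365 start dates. That is 139/365 = 38.1% at 140 days, 167/365 = 45.8% at 168 days and 363/365 = 99.5% at 364 days.

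**2. Year-only stop, both readings.**
- *Full termination date.* With first dose 20 Feb 2022 and termination 16 Aug 2022, stops recorded as 2019, 2020 or 2021 all become 16 Aug 2022. Prior medications turn concomitant.
- *Recorded year kept.* Those stops stay prior. With first dose 20 Sep 2021 and termination 16 Mar 2022, however, a stop recorded as 2021 becomes 16 Mar 2021, before first dose. If the start is recorded as Nov 2021, its imputed date falls after that end, so the check resets it to 16 Mar 2021. An on-treatment event or medication becomes pre-treatment.

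**3. Start with the day missing, both readings.**
- *Full first-dose date.* Every on-treatment day outside the first-dose month gets the wrong month: 141/150 = 94.0%, 139/150 = 92.7% and 149/150 = 99.3% for the three first doses in the order listed. The dosing group is wrong for 90/150 = 60.0%.
- *Day number only.* The recorded month is kept, but the dosing group is wrong for 10, 18 and 29 of 150 days (6.7%, 12.0%, 19.3%). With first dose on 31 March, the rule gives 31 April or 31 June for 30 + 30 = 60 of 150 days.

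**4. The same checks under the rules proposed in the fix.** Contradictions with the recorded year or month fall to 0 in all three scenarios. Dosing-group errors do not disappear:
- Year-only starts: with first dose 20 Sep 2021, 90/150 = 60.0% falls to 43/150 = 28.7%, the 43 days being 19 Nov to 31 Dec 2021. In the two scenarios where dosing lies in one year, it stays at 60.0%.
- Day-missing starts: 10, 12 and 2 of 150 days (6.7%, 8.0%, 1.3%).

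**The case against.** The strongest reply is that little can go wrong in practice. There are two treated subjects, the tables are descriptive, and every date is listed as reported, so any misplacement can be checked by eye. Adverse events are collected prospectively from consent (protocol 13.4), and edit checks with site cleaning apply (SAP 6.3). This stands and sets the severity.

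Several stronger readings are tempting, and the documents do not support them.

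- *That stopped medications simply become concomitant.* This needs the full-date reading of the stop rule. The words about the termination date favour it, but the rule names only the end day and month. The parallel start rule, which sets day and month to 1 January, plainly keeps the year. In addition, general medications are documented only from 30 days before screening (protocol 9.1). Old stop years would arise mainly in disease-treatment history (protocol 12.2), which has its own listing (16.2.4.5). The SAP does not say whether that history feeds the concomitant table.
- *That treatment-emergent counts are broadly wrong.* Treatment-emergent status uses onset only, and a second-year onset normally keeps it. The exception shown is the reset of start to end when the recorded year is kept.
- *That nearly every subject's dosing crosses a year end.* The 99.5% needs a full 52-week course. The study was stopped, and the top exposure category in SAP 10.2 is at least 140 days.
- *That all use of the first-dose date is faulty.* Using it when first dose falls in the recorded month or year is a normal conservative convention. Setting a missing end day to the last day of the month does not contradict the record either.

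**Conclusion.** Wrong as written, low severity. The year-only start rule needs no interpretation: once dosing crosses 31 December, it dates a second-year start in the first year. Its main consequence is the wrong dosing group. The year-only stop rule is ambiguous and can misclassify under both readings, in opposite directions. The missing-day start rule gives either a date in the wrong month or a day with no meaning outside the first-dose month.

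The percentages rest on assumed dates and describe exposure to the fault, not observed errors. A reader might infer that the report's safety tables are in error; nothing in the documents shows that any partial date was recorded. The effect is confined to summary tables, and the dosing-group part to the one subject with two dosing groups.

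**What to change.** Replace the rules in SAP 6.8.2, and through 6.8.3 those for adverse events, with the following.

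- Year-only stop: the earlier of 31 December of the recorded year and the subject's termination date.
- Year-only start: date of first dose only if first dose fell in that year, otherwise 1 January of that year.
- Month-and-year start: date of first dose only if first dose fell in that month, otherwise day 1 of the month.
- General guard: no imputed date, including one produced by the start-equals-end reset, may fall outside the recorded month or year.
- Dosing group: one added rule for partial dates whose recorded period spans both groups. For example, count the record in Total All Doses only and footnote it, or assign it to a prespecified group and footnote it. The other changes do not settle this.

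The cost is a short SAP wording change and a few lines of code, with no new data. If the database holds no partial dates, a sentence in the report saying so closes the point.
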